#### STATEMENT OF PURPOSE, BENEFITS, AND HYPOTHESES:

Rapid weight gain during the first year of life is a strong and consistent predictor of later development of obesity leading researchers and government bodies to call for obesity prevention efforts starting during infancy. Mounting evidence illustrates that bottle-fed infants (whether fed formula or expressed breast milk) are at significantly greater risk for rapid weight gain, gaining an excess of 70-90 grams/month across the first year when compared to their breastfed peers. While the experience of breastfeeding may help mothers develop feeding practices that are responsive to infant satiety cues because they must learn to trust their infants' developing abilities to self-regulate intake, bottle-feeding may facilitate controlling feeding practices due to mothers' abilities to feed in response to the amount of milk in the bottle, leading to overfeeding and excess weight gain.

Public health efforts to date have focused on breastfeeding promotion programs. Regardless, over 50% of US infants are exclusively formula-fed at 6 months of age. Moreover, 40% of breastfed infants receive supplemental formula in a bottle, and 70% receive expressed breast milk from a bottle on a regular basis. Despite the ubiquity of bottle-usage, mothers receive little to no support for learning healthy bottle-feeding practices and a paucity of research has focused on improving bottle-feeding mothers' responsiveness to infant cues. Previous efforts have focused on educating mothers about infant cues and offering less formula during each feeding, but have shown little success in modifying feeding behaviors or weight gain outcomes. Thus, promotion of healthy bottle-feeding practices remains a realistic but under-utilized facet of obesity prevention efforts.

In the proposed research we take a novel, pragmatic approach to promote healthy bottle-feeding. Our previous research has explored whether a simple intervention - covering bottles with an opaque, weighted sleeve – can improve maternal responsiveness

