to infant cues during bottle-feeding. Indeed, in an NIH-funded, laboratory-based trial (R03-HD080730), we illustrated mothers show significantly greater responsiveness and feed their infants 26% less when using opaque, weighted bottles compared to conventional, clear bottles. While initially conceived as a promising adjunct to a larger obesity prevention approach, our laboratory findings suggest that opaque bottles may be a simple, yet potent, stand-alone tool for improving mothers' abilities to feed responsively and reducing infants' risk for overfeeding and rapid weight gain. In the proposed study, we aim to test this approach outside of the laboratory and enroll 100 new, formula-feeding mothers and infants (< 2 weeks old) into a randomized trial to examine the 12-week effects of using opaque, weighted bottles versus clear bottles for improving bottle-feeding interactions and reducing child obesity risk. We will use preestablished and state-of-the-art procedures to objectively measure infants' intake and mothers' responsiveness to infant cues (i.e., objective assessment of feeding patterns, coding of mother-infant bottle-feeding interactions) within their homes at the beginning and end of the 12-week study period. Intervention feasibility, fidelity, acceptability, and safety will be evaluated. Specific aims of the proposed research are:

AIM 1: To test the hypothesis that mothers who use opaque, weighted bottles for a 12-week intervention period will feed their infants less and be more responsive to their infants' cues compared to mothers who use clear bottles. Intake will be objectively assessed via change in bottle weight before and after feeding observations. Responsiveness to infant cues will be coded from video-records of feeding observations using the Nursing Child Assessment Parent-Child Interaction Feeding Scale.

AIM 2: To test the hypothesis that infants who are fed from opaque, weighted bottles will exhibit slower 12-week weight gain trajectories compared to infants who are fed from clear bottles. Infants' weight, length, skinfolds, and waist circumference will be measured at the beginning and end of the study; weight-forlength z-scores (WLZ) will be calculated using the WHO Growth Standards.

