#### **METHODS:**

#### **Design and Sample**

Design. We have designed a 12-week randomized clinical trial to explore the efficacy

and feasibility of a 12-week opaque, weighted bottle intervention. Previous research suggests that, during early infancy, 12 weeks is a sufficient duration of follow-up to capture divergences in growth trajectories related to feeding mode, and that the window between 12-24 weeks is when associations between feeding mode and excess weight gain emerge. Mother-infant dyads will be randomized to use conventional, clear bottles (*clear* group) or opaque, weighted bottles (*opaque* group). Dyads will participate in home-based assessments of bottle-feeding interactions at study entry and 12 weeks, with brief assessments at 2 and 6 weeks.

**Subjects and Recruitment.** A total of 100 mother-infant dyads will participate. We will use recruitment methods similar to those effectively used in our previous research. Mothers will be recruited through ads in local newspapers; targeted social media ads; Women, Infant & Children (WIC) offices; OB/GYN and pediatrician offices; mass mailings; online sites; and a list of past participants who have asked to be notified of future studies. See **Appendix 1** for example recruitment materials.

Given San Luis Obispo and Santa Barbara Counties are predominately White and Hispanic (66% White, 35% Hispanic, 2% Black, and 4% Asian), we will over-sample Black mothers to increase sample diversity (targets: 55% White, 35% Hispanic, 13% Black, 4% Asian). Both English and Spanish-speaking mothers and their healthy, term infants of either sex will be eligible.

Inclusion criteria for the dyads include:

- 1) mothers 18-40-years of age
- 2) infants <8-weeks of age
- 3) mother is planning to bottle-feed, or is currently bottle-feeding, her infant
- 4) mother predominantly or solely responsible for infant feeding
- 5) dyad has a pediatrician and plans to attend infant well-visits
- 6) mother is willing to use stainless-steel bottles and to provide the study will her current bottles, which would be returned after study completion
- 7) prior to the introduction of solid foods

To protect infants who might be at risk for underfeeding or inadequate growth, exclusion criteria for infants include known risk factors:

- 1) preterm birth (i.e., gestational age <37 weeks)
- 2) low birth weight (<2500 g)
- 3) maternal smoking during pregnancy

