#### **Statistical Considerations**

Data Analysis. All quantitative analyses will be conducted using SAS v.9.4 (SAS Institute Inc., North Carolina, USA). Oualitative interview data will be transcribed and sorted into thematic categories using constant comparison within the framework of grounded theory. We will use linear regression to model the change in infant intake and maternal responsiveness (Aim 1) and change in WLZ, skinfolds, waist circumference (Aim 2) by the primary study variable of *clear* versus *opaque* group. For Aim 3, we will examine the feasibility, fidelity, adherence, acceptability, and safety of the intervention by summarizing quantitative and qualitative data related to recruitment and retention, mothers' use of their assigned bottles, perceptions of and barriers to using the bottles, and any issues related to infant inadequate weight gain or weight loss. We will then explore whether variations in intervention feasibility, fidelity, adherence, acceptability or safety are correlated with baseline characteristics of mothers (e.g., weight status, race/ethnicity, socioeconomic status, parity, feeding practices and styles, non-maternal caregiver involvement in feeding) and infants (e.g., sex, birth weight, weight status, temperament). Finally, we will assess whether the effects of the intervention on infant intake, maternal responsiveness, and infant WLZ change are moderated by the following factors: nipple type; mothers' adherence to the intervention, race/ethnicity, parity, or feeding practices and styles; infants' sex, temperament, and timing of solid food introduction; and the extent to which non-maternal caregivers are feeding the infant. Moderation will be explored by including a group by moderator interaction term in the linear regression models used to explore Aims 1 and 2. All inferential analyses will be preceded by appropriate descriptive statistics and graphs to determine that assumptions for linear regression are satisfied.

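### The protocol names two different feeding populations, and baseline share of feeds by bottle, which scales exposure and is probably prognostic, is absent from the Aim 2 models

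*Combined protocol and SAP*

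**What the plan says.** The Statement of Purpose, Benefits, and Hypotheses says the study will "enroll 100 new, formula-feeding mothers and infants (< 2 weeks old) into a randomized trial". Under Design and Sample, inclusion criterion 3 reads "mother is planning to bottle-feed, or is currently bottle-feeding, her infant" and criterion 2 reads "infants <8-weeks of age". No inclusion or exclusion criterion sets a milk type, a minimum share of feeds by bottle, or a limit on feeding at the breast.

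The background refers to "bottle-fed infants (whether fed formula or expressed breast milk") as one group. It reports that this group gains 70-90 g/month more than breastfed peers over the first year. It also describes mixed feeding as common: "40% of breastfed infants receive supplemental formula in a bottle", and "70% receive expressed breast milk from a bottle on a regular basis".

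Under Experimental Conditions, the assigned bottles are to be used for every bottle feed. Feeds at the breast are outside the intervention.

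Under Assessments and Measures, infant feeding history (Appendix 7) is listed among the additional potential moderators. The only named covariate is nipple flow rate. The Data Analysis text regresses change on group. Its moderator list covers nipple type, adherence, race/ethnicity, parity, feeding practices and styles, infant sex and temperament, and "timing of solid food introduction; and the extent to which non-maternal caregivers are feeding the infant". The Randomization paragraph mentions no stratification.

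**The concern.** The purpose section and the eligibility criteria describe different samples, both in how the infant is fed and in age at entry. A reader cannot tell to whom the result will apply.

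The feeding difference also matters for the analysis. An infant fed mostly at the breast, with an occasional bottle, meets criterion 3. For that infant the assigned bottle can influence only a small part of intake, so any effect on 12-week growth should be smaller. By the protocol's own background, feeding mode also predicts weight gain in its own right. A baseline variable that may both scale exposure and predict outcome is a natural covariate and moderator. From the feeding history, only the timing of solid foods reaches the analysis plan. Feeding practices and styles does not clearly fill the gap, because the named style instrument (IFSQ) measures maternal behaviors and beliefs, not feeding route.

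At stake are the power and precision of the WLZ, skinfold and waist comparisons, and the meaning of the average effect that they estimate.

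**Working it through.** **Inputs from Power calculations:** n = 100; SD of WLZ = 1.0; correlation between baseline and 12 weeks = 0.45; alpha = 0.05; detectable difference = 0.59 at 80% power. **Assumed, because not stated:** 1:1 allocation (50 per arm) and a two-sided test.

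**Step 1: reproduce the plan's figure.**
- SD of change = 1.0 × √(2 × (1 − 0.45)) = √1.10 = 1.049.
- Standard error of the difference = 1.049 × √(2/50) = 0.210.
- Detectable difference = (1.960 + 0.842) × 0.210 = 0.588 by the normal approximation, or 0.594 using the t distribution.
- Power at 0.59 = Φ(0.59/0.210 − 1.960) = 80.3%.

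The stated 0.59 is reproduced, with essentially no reserve.

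**Step 2: illustrate dilution.** The documents give no share of feeds by bottle in the expected sample, so this step rests on two further assumptions: that a fully bottle-fed sample would have a true difference of 0.59, and that the effect is proportional to the mean bottle share b. The mean difference is then 0.59 × b.

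| Mean bottle share b | Difference | Power, 50 per arm | Total N for 80% power |
|---|---|---|---|
| 1.0 | 0.590 | 80.3% | 100 |
| 0.9 | 0.531 | 71.6% | 124 |
| 0.8 | 0.472 | 61.4% | 156 |

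The same can be put as a mixture of dyads, with the remainder fully bottle-fed:
- If 10% of dyads give only 20% of feeds by bottle, b = 0.90 + 0.10 × 0.20 = 0.92, the difference is 0.543 and power is 73.5%.
- If 25% do, b = 0.75 + 0.25 × 0.20 = 0.80 and power is 61.4%, as in the table.

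**Step 3: what an interaction test can show.** Take a two-level moderator split evenly, so 25 dyads per group-by-level cell. The standard error of the interaction is 1.049 × √(4/25) = 0.420, twice that of the main comparison. The interaction detectable at 80% power is therefore 2 × 0.588 = 1.18 WLZ units. A moderation analysis at n = 100 can only be exploratory.

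**Step 4: which aims are affected.** Aim 2 outcomes accumulate over all feeds for 12 weeks, so bottle share acts on them directly. Aim 1 intake and NCAFS scores are taken during an observed bottle feed. A low bottle share can affect those only indirectly, through less practice with the assigned bottle.

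**The case against.** The best defence is that broad eligibility is a legitimate choice in a pilot-feasibility trial. The title and background speak of bottle-fed infants and include expressed milk, so the purpose section's formula-feeding wording is the outlier. Formula-feeding also does not mean exclusively formula-fed, so aligning the wording would not by itself exclude mixed feeders. All of this stands, and the point does not require narrower eligibility.

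Four stronger readings are tempting, but the documents do not support them.

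- *That the power statement assumes a full effect in every infant, so true power is far below 80%.* The plan gives 0.59 as a detectable difference, not as the expected effect under full exposure. No low bottle share appears in the documents. Some procedures suggest established bottle use, though they do not require a high share: mothers hand over their current bottles, and visits are timed around a usual bottle feed.
- *That a null result could not be told apart from low exposure.* A tracking device on the bottles in both groups is meant to record the time and volume of each bottle feed, and mothers report use of the assigned bottle at 2, 6 and 12 weeks. These are exposure data. Their limits are that they are mainly post-randomization, that the device is described as still under development, and that the denominator of the self-reported percentage is not defined.
- *That mothers who only plan to bottle-feed cannot supply the week-1 feeds.* Planning at screening does not mean no bottle use by Pre-Test 1. Both pre-tests film a bottle feed, and mothers learn their group only at the end of the second. The procedure therefore already requires some bottle use.
- *That the comparison is biased.* Randomization balances feeding mode on average. What remains is chance imbalance.

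It is also fair to say that a covariate cannot restore a diluted mean difference. It can improve precision and clarify interpretation.

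**Conclusion.** The point holds in a limited form. The purpose section and the inclusion criteria name different populations, by feeding mode and by infant age. Baseline feeding mode, which plausibly scales exposure and which the protocol's background treats as prognostic for weight gain, has no place in the planned models, although a feeding history is collected.

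The consequence is mainly for Aim 2: possible dilution, lost precision and an unclear target population. The size cannot be fixed from the documents. The falls from 80% to about 72% (mean share 0.9) and 61% (mean share 0.8) are illustrations. They depend on a true full-exposure difference of 0.59, strict proportionality, 1:1 allocation and a two-sided test. The prognostic argument has its own limit: the background figure concerns weight gain in grams, not WLZ change over 12 weeks, so the gain in precision is likely but not quantified.

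**What to change.** 1. Reconcile the Statement of Purpose with the inclusion criteria, so that both name the same feeding population and the same age at entry.
2. Record at baseline the share of daily feeds given by bottle, within the existing feeding history. Appendix 7 is not available here and may already ask this; if so, nothing need be added.
3. In Data Analysis, include that baseline share as a covariate in the Aim 2 models (WLZ, skinfolds, waist circumference). For Aim 1 it is optional.
4. Name it as a pre-specified baseline moderator, labelled exploratory because of the low power of an interaction test at n = 100.
5. In Power calculations, state that the detectable difference of 0.59 applies to the average effect in the enrolled mix of feeding modes.

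The cost is wording, at most one added question and one model term, plus one exploratory interaction. If the broad eligibility is kept, recruitment need not change. These steps make the estimate more precise and easier to interpret; they do not recover power lost to dilution.

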#### **Experimental Conditions**

- 1. Control Group: Conventional, Clear Bottles: These mothers will receive usual care from their pediatric providers and each mother will be given 12 conventional, clear bottles of various sizes (4-12 ounces) that are compatible with a variety of different nipples manufactured by leading bottle companies. Mothers will also be given a handout about paced bottle-feeding (see Appendix 3), which includes messages about feeding in response to infant cues.
- 2. Intervention Group: Opaque Bottles: These mothers will receive everything provided to the *clear* group, but will instead receive 12 opaque, weighted bottles of various sizes (4-12 ounces). These bottles will be stainless steel (Pura Kiki, California, USA) and compatible with a variety of different nipples manufactured by leading bottle companies. These bottles weigh ~70g more than comparable plastic bottles, which is similar to the amount of added weight used in our pilot work. Mothers in the intervention group will also receive a handout about how opaque bottles can help them attend to infant cues.

For both groups, we will replace *all* of the mother's current bottles with study bottles and will ensure that the study bottles match the size of the bottles the mother currently uses; we will also supply any additional bottles needed for infant care in other settings (e.g., child care). Mothers will be asked to use the study bottles for all bottle feedings, regardless of whether the mother or another caregiver is feeding the infant. Monthly phone calls from the study interventionist will query about any need to replace bottles or any feeding difficulties; we will also instruct the mother to contact us if she needs more bottles. We anticipate that the features of allowing mothers to continue using their preferred nipple and replacing all of the mothers' bottles with study bottles will encourage compliance.

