- Maternal responsiveness to infant cues will be objectively assessed by video-coding of all feeding observations. After each visit, three trained coders who are unaware of the experimental conditions and hypotheses of the study will code videos using the NCAFS, a reliable and valid means of observing and rating mother-child interactions during a feeding session. The NCAFS is validated for use with mothers and their 0-1-year-old infants, can be applied to a breast or bottle-feeding episodes, and has been used during both lab- and home-based feeding observations. It contains 76 observable behaviors that are organized into six subscales; for the proposed research, we will

focus the Maternal Sensitivity to Infant Cues subscale. Reliability will be established prior to full coding of all videos. To this end, coders will code 10 common videos, and will double-code 10 additional videos. Inter-coder comparison of the 10 common videos will be used to establish inter-coder reliability. Intra-coder comparison of the 10 double-coded videos will be used to establish intra-coder reliability. Full coding will not commence until a Kappa > 0.80 is reached for all coders. The PI is certified in this coding system and has it previously.

- Maternal feeding style, including responsive and pressuring feeding, will also be subjectively assessed at study entry and completion using the Infant Feeding Style Questionnaire (IFSQ; see Appendix 4), which assesses maternal behaviors (e.g., control) and beliefs (e.g., concern about feeding) related to infant feeding. This scale has been validated in diverse samples of mothers with young infants and the PI has used this measure in previous research.
- Infant growth will be assessed during all home-based assessments by trained research assistants measuring infant weight and height in triplicate using a portable infant scale/infantometer (models 334 and 233; Seca, Hamburg, Germany). To minimize bias, infants will always be weighed and measured while only wearing a clean diaper and prior to the observed feeding. We will use the World Health Organization (WHO) Anthro software version 3.0.1 (http://www.who.int/childgrowth/en/) to calculate age-and sex-specific weight-for-length z-scores (WLZ) based on the WHO growth standards. We will also assess infant adiposity by infant skin-fold thickness and waist circumference using standard protocols.

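### The opaque arm alone gets a second handout on infant cues, so the 12-week group contrast estimates bottle plus extra handout, not bottle type alone

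*Combined protocol and SAP*

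**What the plan says.** Experimental Conditions describes the education in three steps. For the clear group: "Mothers will also be given a handout about paced bottle-feeding (see Appendix 3), which includes messages about feeding in response to infant cues". For the opaque group: "These mothers will receive everything provided to the *clear* group, but will instead receive 12 opaque, weighted bottles of various sizes (4-12 ounces"). Then, for the opaque group only: "Mothers in the intervention group will also receive a handout about how opaque bottles can help them attend to infant cues".

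The research question is worded around the bottle. The Statement of Purpose says that "our laboratory findings suggest that opaque bottles may be a simple, yet potent, stand-alone tool for improving mothers' abilities to feed responsively", and that the trial will "examine the 12-week effects of using opaque, weighted bottles versus clear bottles for improving bottle-feeding interactions and reducing child obesity risk". Aims 1 and 2 compare opaque with clear bottles, and the Power calculations paragraph describes both aims in terms of bottle type.

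For maternal responsiveness, the Measures section says the study will "focus the Maternal Sensitivity to Infant Cues subscale" of the NCAFS. Feeding style is also self-reported on the IFSQ at entry and completion. The Data Analysis paragraph models change by linear regression on clear versus opaque group.

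**The concern.** The arms differ in two things: the bottle, and one additional sheet about using it to attend to cues. A single group coefficient cannot separate them, and the analysis plan has no other step that does.

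This matters most where the sheet and the outcome overlap. The chosen NCAFS subscale rates how sensitively the mother responds to cues, and the extra sheet is about attending to cues. Mothers are told their group at the end of Pre-Test 2 and are filmed again at week 12. Coders who are unaware of condition guard against biased scoring, but not against mothers behaving differently because of what they have read. The self-reported IFSQ is exposed in the same way.

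A positive result on maternal sensitivity would then support a claim about the bottle that the contrast cannot carry by itself. A later, larger trial or a public-health message could credit the bottle with an effect that partly belongs to a leaflet.

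**Working it through.** **Step 1: what each arm receives (Experimental Conditions).**

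| Component | Clear | Opaque |
|---|---|---|
| 12 study bottles | clear | opaque, weighted |
| Paced-feeding handout with cue messages | yes | yes |
| Handout linking opaque bottles to attending to cues | no | yes |

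The second row cancels in the group contrast. The first and third do not. The group coefficient is therefore the joint effect of bottle and extra sheet.

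**Step 2: what standard error applies to NCAFS change.** Inputs from Power calculations: SD 1.91; baseline to week-12 correlation .55 (clear) and .40 (opaque); α = .05; 100 dyads. Assumed here: equal allocation (50 per arm) and a two-sided test.

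Variance of change = 2 × SD² × (1 − r):
- clear: 2 × 1.91² × 0.45 = 3.283
- opaque: 2 × 1.91² × 0.60 = 4.378

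SE of the group difference = √[(3.283 + 4.378)/50] = 0.391.

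Difference detectable with 80% power = (1.960 + 0.842) × 0.391 = 1.10 points. The protocol states 1.32, so its NCAFS figure does not reproduce from its own inputs. The same method gives 19.3 mL for intake (stated 19.1) and 0.588 for WLZ (stated 0.59), so the method appears to be the one used for those two outcomes. Working back from 1.32, the implied SE is 1.32/2.802 = 0.471. Both SEs are carried forward.

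**Step 3: illustration under assumed handout effects.** Suppose the bottle has no effect on the NCAFS subscale and the extra sheet raises the score by δ. The chance of a significant group difference is the two-sided rejection probability of a t test with 98 degrees of freedom and noncentrality δ/SE.

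| Assumed δ (points) | δ/1.91 (SD units) | SE 0.391 | SE 0.471 |
|---|---|---|---|
| 0 | 0 | 5% | 5% |
| 0.25 | 0.13 | 9.7% | 8.2% |
| 0.50 | 0.26 | 24.4% | 18.3% |
| 0.75 | 0.39 | 47.5% | 35.1% |

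None of the non-zero δ values comes from the documents.

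**Step 4: does another part of the design isolate the bottle?** The assessment table has each mother observed with both bottle types at week 1 and again at week 12, counterbalanced. Group is disclosed only at the end of Pre-Test 2. Provided the group-specific sheet is not given before disclosure, the week-1 within-mother contrast of clear against opaque is free of it. That contrast measures an immediate effect, not 12 weeks of use, and Data Analysis does not plan it for this purpose. At week 12 the opaque-arm mothers have had the sheet whichever bottle is in hand.

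**The case against.** Several points on the other side have force.

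- **Both arms get cue education.** A reader might infer that controls receive nothing on infant cues. The text contradicts that: the shared handout carries such messages. Only an increment differs. Neither handout's text is in the documents, so the size of the increment cannot be judged. This stands, and it narrows the concern without removing it.
- **Education may do little.** The Statement of Purpose reports that earlier efforts to teach mothers about cues and to offer less formula had little success in changing feeding behaviour. This stands as a reason to expect a small handout effect. It does not show a zero effect, and if the sheet is inert, equalising it loses nothing.
- **Expectancy is not specific to the sheet.** Mothers cannot be blinded to their assigned bottle, so removing the sheet would not remove expectation effects. This stands. The point made here concerns unequal education, not blinding.
- **It is a package in a pilot-feasibility trial.** Aim 3 refers to a bottle intervention, Experimental Conditions lists the handout openly, and brochure distribution is tracked in each group. A package is a legitimate thing to test. But Aims 1 and 2 and the power section name only the bottle.
- **The stand-alone phrase is a premise, not a conclusion.** It reports what laboratory findings suggest. That is fair, and the protocol contains no conclusion yet. The same section nevertheless says the study will test this approach outside the laboratory.

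**Conclusion.** The concern holds in a limited form. The planned 12-week group contrast estimates opaque bottle plus an extra cue-focused handout, while Aims 1 and 2 and the power section describe it as an effect of the bottle. Exposure is greatest for NCAFS sensitivity to cues and the IFSQ.

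The size of any handout effect cannot be derived from the documents. The figures of 8–10%, 18–24% and 35–48% are conditional on assumed effects of 0.25, 0.50 and 0.75 points, equal arms of 50 and a two-sided test. They show the risk of crediting the wrong component. They should not be read as an inflated type I error for the comparison actually randomised, which remains a valid test of the package.

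A reader might also infer that the design can say nothing about the bottle alone. That goes too far: the week-1 within-mother observations give a handout-free contrast, though an acute one that the plan does not use in this way.

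**What to change.** Preferred: keep cue-attention messages only in the paced-feeding handout that both arms already receive, without reference to opaque bottles. Make any second sheet a practical one on the assigned bottle (for example cleaning and nipple fit), of the same length in each arm. The cost is editing and printing one sheet per arm. The small downside is that the contrast between arms may narrow slightly.

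Alternative: if the opaque-only handout is kept, define the intervention in Aims 1 and 2, the power section and the reported conclusions as opaque bottle plus handout, and make no stand-alone bottle claim from the 12-week group contrast. The cost is rewording only.

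Optional under either choice: name the week-1 within-mother clear-versus-opaque contrast as a supporting analysis, labelled as an acute effect. It uses data already being collected.
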